- c. Most studies identified clinical and procedural predictors of non-attendance. Most conducted multivariable analyses, but only one study (Blumenthal) developed and validated a clinical prediction rule for missed endoscopy appointments. Patient-level predictors of missed or cancelled appointments in multiple studies included: minority race or ethnicity, unmarried/unpartnered, Medicaid or no health insurance, and presence of a mental health or substance abuse disorder. The clinical indication for the procedure was a predictor in some but not all studies. Clinic and system-level predictors included: longer wait time between scheduling and procedure; prior missed endoscopy appointments, and prior missed appointments in other settings. A large VA study also found substantial variation between VA facilities. (Partin) The one reported prediction rule incorporated patient-level and system-level variables and had a c-statistic of 0.75 in the development set, and 0.70 in the validation set, indicating moderate accuracy in discriminating individuals at high risk of missing endoscopy appointments from those at lower risk. (Blumenthal)
- d. Some form of reminder (letter or phone call) was commonly provided as a baseline in these studies. One randomized trial compared a “live” nurse reminder call to IVR

outreach 3 days or 7 days prior to the endoscopy appointment – no differences were found between groups. (Griffin) A before-after study found that no-shows decreased from 16.5% to 12.8% after instituting a nurse call. This study also quoted the lost revenue from a missed appointment as approximately \$1000 for colonoscopy and \$780 for upper endoscopy. An RCT of a telephone call 1 day prior to colonoscopy to educate about bowel prep showed that adequate prep was greater in the intervention than control group (81.6% vs. 70.3%), as was polyp detection (38.0% vs. 24.7%).

e. In summary

- The prevalence of missed endoscopy appointments or late cancellations is already lower in KPCO than in most published studies.
- The most important clinical predictors used in other studies are available through KPCO electronic data sources.
- The only reported prediction rule to identify high-risk patients for missing endoscopy appointments had only moderate accuracy.
- A relevant randomized trial showed no difference between a single “live” reminder and a single IVR call 3 days or 7 days prior to the visit.

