- For the duration of this intervention, the GI clinic will discontinue all live pre-procedure reminders so that we can assess the effectiveness of a purely automated intervention. Staff will continue post-procedure calls to assess service quality. Selective live reminders for members at high risk of missed appointments will be assessed in Step 3 of this project.

Intervention delivery: All interventions by email, text and telephone will be delivered by secure messages from the Automated Communication Technology (ACT) team in the KPCO

Institute for Health Research. At present, GI clinic nurses or staff make live reminder calls to some members as time allows; these calls will be stopped for the duration of the Step 1 trial.

Over the 6-month period of the project, we estimate that approximately 2300 visits per month will be scheduled across the 3 participating sites. After anticipated exclusions (10% of total cases), we estimate that there will be approximately 2100 eligible appointments per month. We project that the study will run from March 8, 2019 through September 7, 2019 to achieve the proposed sample size of approximately 13,000 appointments. The duration of the study will be dictated by the number of appointments necessary to detect an operationally significant reduction in the rate of appointment loss, as described in the sample size calculations below. We will monitor recruitment during the study and adjust the duration of the randomization period as necessary to achieve the projected sample size.

9. Study Measures

Outcome variable: The primary outcome for the study will be “appointment loss”, defined by GI leaders as the combined rate of prior day cancellations, same-day cancellations, and missed clinic appointments (“no shows”). The rationale for this outcome definition is that it is difficult to schedule new procedures within this time frame. As a secondary outcome, we will assess the adequacy of the bowel preparation for colonoscopy only.

Covariates: To describe the project participants and identify clinically and operationally relevant subgroups, we will measure patient covariates that we have used in prior IVR-T evaluations in primary care clinics, as well as variables specific to the GI clinic setting. These variables are listed in Appendix 1. All variables will be drawn from the IHR Virtual Data Warehouse (VDW), KPCO appointment scheduling system, or endoscopy data from Clarity.

10. Sample size and statistical analysis

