1. We will develop a multivariable logistic regression model to predict appointment loss using approaches similar to prior IVR-T interventions. Clinic site will be included as a fixed effect. We will include linear and quadratic terms for continuous predictors and include both terms in the final model if statistically significant. Missing values for each predictor will be included as a separate category. Backward selection with Wald chi-square tests will guide the selection of predictors. The final prediction model will include an indicator variable for treatment group and all covariates with *p*-values <0.05. The discrimination of the model will be assessed with the *c*-statistic. We will use this prediction rule to stratify participants into risk quartiles and will assess the effectiveness of the intervention in each quartile.
2. We will assess the effectiveness of the intervention in each of the 3 participating clinics, after adjusting for predictors of missed appointments/late cancellations, to provide preliminary information on site-level factors that may modify intervention effectiveness.
3. We will analyze the effectiveness of the intervention in the subgroup of individuals who schedule their endoscopies \leq 7 days prior to the procedure, since these individuals will receive no reminders under the standard protocol.

Human subjects

The standard reminder protocol includes a text message that “rolls over” to an IVR automated phone if the text cannot be delivered. The GI Clinic has received permission from the KPCO Compliance Office to send emails to the private email addresses of KPCO members.

Study Risks: This study utilizes current standard protocols for contacting KPCO members and data collected during the course of routine clinical care to improve efficiencies in the delivery and quality of care for patients. Therefore, the primary risk of this study is the potential for loss of confidentiality and privacy of a member, through a loss or inappropriate disclosure of study data. There are no known risks to investigators or staff.

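### The appointment-loss risk rule is selected, fitted, assessed and cut into quartiles on the same trial visits, so its c-statistic and quartile spread will on average be modestly too favourable

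*Combined protocol and SAP*

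**What the plan says.** Section 10, planned subgroup analysis 1, sets out the steps in order:

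- Candidate terms: "We will include linear and quadratic terms for continuous predictors", and "Missing values for each predictor will be included as a separate category".
- Selection: "Backward selection with Wald chi-square tests will guide the selection of predictors".
- Final model: "The final prediction model will include an indicator variable for treatment group and all covariates with" p-values below 0.05.
- Performance: "The discrimination of the model will be assessed with the" c-statistic.
- Use: "We will use this prediction rule to stratify participants into risk quartiles", with the intervention effect then assessed in each quartile.

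Because the final model contains a treatment-group indicator, it has to be fitted on the randomized visits. Appendix 1 supplies the candidates: 28 variables once the appointment outcome and bowel-prep adequacy are set aside. Five of them are listed as both a number and a rate, and most categorical variables have no stated number of levels.

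The literature review (item c) describes the one published endoscopy rule, which "had a c-statistic of 0.75 in the development set, and 0.70 in the validation set".

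**The concern.** A model chosen by p-value and then assessed on the data that chose it partly fits noise. Its c-statistic in those data exceeds, on average, what it would achieve in new visits. Quartiles cut from the same score also look further apart than they are: observed loss is too high in the top quartile and too low in the bottom one.

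What is at stake is how well the rule is said to separate members by risk. The plan foresees publication and sharing of results with organizational sponsors. Its literature review calls the published rule only moderately accurate, citing both development and validation figures. A KPCO c-statistic with no correction would be the counterpart of the 0.75, but could easily be read against the 0.70.

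**Working it through.** **Plan's own figures.** The documents give no expected c-statistic or quartile spread, so there is none to reproduce. The 6.8% loss rate does reproduce from the Table 1 totals: 7,612 × 9.2% + 7,592 × 4.8% + 9,283 × 6.5% = 700 + 364 + 603 = 1,668 (before rounding of terms), and 1,668 / 24,487 = 6.81%.

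**Events.** With a 20% relative reduction (6.8% vs 5.4%, Table 3) the average loss is (6.8 + 5.4)/2 = 6.1%.

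- N = 11,112 (Table 3): 11,112 × 0.061 = 678
- N = 13,000 (planned total): 13,000 × 0.061 = 793
- N = 13,000 with no effect: 13,000 × 0.068 = 884

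Analysis is restricted to each member's first randomized visit, so the analysed N may fall below 13,000. N = 11,112 serves here only as a lower value; whether Table 3 is right is a separate matter.

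**Candidate parameters.** Appendix 1 does not fix the number, so I assumed 40 to 100. At 6.1% loss, events per parameter run from 678/100 = 6.8 to 793/40 = 19.8.

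**Simulation of the planned procedure.** The logistic model had the treatment indicator forced in, backward Wald elimination at p < 0.05, mean loss 6.1%, and independent predictors (half binary). True c was about 0.65 to 0.745, with 20 replicates per setting. Optimism = c in the trial visits − c of the same rule in 40,000 new visits. Gap = loss rate in quartile 4 − loss rate in quartile 1, with the trial's cut-points applied to the new visits. Ranges cover both values of N and all predictor strengths.

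| Candidates (truly predictive) | Mean optimism in c | Inflation of gap (points) |
|---|---|---|
| 40 (12) | 0.006–0.017 | 0.3–0.8 |
| 60 (15) | 0.009–0.017 | 0.4–0.9 |
| 100 (20) | 0.016–0.021 | 0.8–1.4 |

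The SD of optimism between simulated trials was 0.008 to 0.015. Apparent gaps were about 8 to 13 points.

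**Less favourable settings** (80 candidates, 25 truly predictive):

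- N = 13,000: c 0.661 vs 0.635 in new visits (0.026); gap 8.4 vs 7.0 points (1.4).
- N = 11,112: c 0.653 vs 0.619 (0.034); gap 8.0 vs 6.1 points (1.9); top-quartile loss 10.7% vs 9.5%.
- N = 11,112, a separate run with weak predictors: c 0.670 vs 0.634 (0.036); top-quartile loss 11.5% vs 10.3%.

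**Does correction work?** Both methods below repeat the whole selection in every resample or fold.

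| Setting | Apparent c | Bootstrap | 10-fold | New visits |
|---|---|---|---|---|
| N = 13,000, 60 candidates | 0.686 | 0.668 | 0.674 | 0.674 |
| N = 13,000, 80 (25) | 0.661 | 0.631 | 0.637 | 0.635 |
| N = 11,112, 80 (25) | 0.653 | 0.617 | 0.622 | 0.619 |

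A further small bootstrap run (N = 13,000, 60 candidates, 8 datasets, 30 resamples each) over-corrected: apparent 0.704, corrected 0.686, new visits 0.696. There the corrected value was no closer than the apparent one. Quartile loss rates from cross-validated scores nearly matched those in new visits.

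**The case against.** The case against is mainly about size and consequence, and much of it stands.

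- **The bias is small and not certain in one trial.** With 28 parameters and N = 13,000, mean optimism was 0.009 with an SD of 0.012. A single trial could show none. This stands.
- **The parameter count is not in the documents.** Appendix 1 is a working list with open questions, and some forms of a variable may be alternatives rather than joint terms. This stands, which is why a range is used.
- **Validation may be implied.** The plan says it will follow its earlier IVR-T work, and the title of one cited trial paper mentions validating a predictive model. Neither commits this trial to validating this rule; the listed steps end with the c-statistic and the quartiles.

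Stronger readings are tempting but not supported:

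- A reader might infer that an inflated rule will choose who gets live calls. The protocol says only that "Selective live reminders for members at high risk of missed appointments will be assessed in Step 3 of this project"; it does not say that this rule, its c-statistic or its quartiles will be used.
- A reader might take the published fall from 0.75 to 0.70 as the fall to expect here. The documents give neither that study's size nor its validation design, and 0.05 exceeds every mean optimism simulated above.
- A reader might infer that the trial's effectiveness result is compromised. The randomized primary comparison does not depend on the rule, and nothing here shows bias in the treatment effects within quartiles.

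**Conclusion.** The point holds in a modest form. Followed as written, the plan yields a c-statistic that is on average about 0.006 to 0.02 too high, and up to about 0.035 too high if there are many weak predictors. The difference in loss between the extreme quartiles is about 0.3 to 2 percentage points too wide. These sizes rest on 40 to 100 candidate parameters, independent simulated predictors, roughly 680 to 880 events and true discrimination near that of the published rule or somewhat below. The direction follows from the design of the analysis; the exact size cannot be known from the documents. The consequence is a reporting defect in a planned subgroup analysis: the uncorrected c-statistic should not be set beside the validated 0.70. It is worth correcting because the remedy is cheap.

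**What to change.** Add to planned subgroup analysis 1:

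1. Report, beside the apparent value, an optimism-corrected c-statistic and a calibration slope. Use either a bootstrap or 10-fold cross-validation, repeating the entire backward selection, including the decision on quadratic terms, in each resample or fold.
2. Form the risk quartiles, and report their observed loss rates, from the cross-validated (out-of-fold) risk scores.

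Shrinking the apparent score is not a substitute for step 2. Multiplying every score by one positive factor leaves the ranking unchanged, and so also quartile membership, the c-statistic and the observed quartile loss rates.

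The cost is some extra programming and a slightly lower stated c-statistic; no further members are needed. The bootstrap may slightly over-correct, as the runs above show, so cross-validation is a reasonable default.

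A rule derived on the January to mid-October 2018 visits and applied unchanged to the trial should be at most a sensitivity analysis. It would have more events (about 1,668 from the Table 1 totals). But live nurse calls were then in use, most often at Rock Creek, eligibility differs (no first-visit restriction or stated lead-time exclusion), and covariates would have to be extracted. The printed Lone Tree components also sum to 1.2 + 1.0 + 3.2 = 5.4%, not the 6.5% total, which would give about 1,566 losses instead.

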- Another randomized trial suggests that a live call the day prior to the procedure can increase the adequacy of the bowel prep.

PROJECT QUESTIONS AND HYPOTHESES

This project will address the following question:

Does an “enhanced” IVR-T protocol differ in effectiveness from the standard IVR-T protocol in reducing missed appointments and late cancellations for GI endoscopy?

Hypothesis 1: The enhanced IVR-T protocol will be more effective.

RESEARCH DESIGN AND METHODS

We will conduct a randomized trial over a 6-month period (March through September 2019) in the 3 GI endoscopy clinics (Franklin, Rock Creek, and Lone Tree). All members currently receive a text reminder 7 days prior to their procedure, which rolls over to a telephone reminder if the text cannot be delivered or the member’s phone is not text-enabled. Members will be randomized either to receive this standard IVR-T protocol or to receive an enhanced reminder protocol.

Inclusion criteria:

- a. Members scheduled for any GI procedure (upper endoscopy, colonoscopy, or both), with or without anesthesia, at all three clinical sites (Franklin, Rock Creek, Lone Tree) will be included if their procedure is scheduled \geq 2 days prior to the procedure. The IVR-T protocol will be adapted based on the wait time between appointment scheduling and the date of the procedure.
- b. Members with all clinical indications (screening, diagnosis, or surveillance), will be included.

Exclusion criteria:

- a. KPCO members who request not to participate in research or not to receive IVR-T or email outreach
- b. KPCO members in the “break the glass” or “code pink” protocols.
- c. Members whose procedure is scheduled $<$ 2 days prior to the procedure.

Randomization: Beginning in March 2019 (or on completion of all necessary design steps), we will use the randomization algorithm in the Structured Query Language program that manages the IVR relational database to assign each visit for a procedure at all three sites to one of the two interventions. Since members with multiple procedures on different days during the study period could receive different interventions for different visits, we will limit the statistical analysis to the first randomized appointment during the project period. Randomization will be stratified by clinic site.

Intervention content

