Sample size calculation: As shown in Table 1, “appointment loss” in the 3 GI clinics has been 6.8% from January – mid-October 2018. Across sites, approximately 2580 procedures/month were scheduled, and 175 were missed. Using standard parameters for Type 1 error (0.05, two-sided) and Type 2 error (0.20), the necessary sample to detect differences between standard and enhanced IVR-T protocols is:

Table 3. Sample Size Estimates

Detectable difference in appointment loss	N total (per group)	Duration of project (months)
3% absolute difference (6.8% vs. 3.8%)	2654 (1327)	1.3
2% absolute difference (6.8% vs. 4.8%)	5644 (2822)	2.7
1% absolute difference (6.8% vs. 5.8%)	21244 (10622)	10.1
20% relative difference*	11112 (5556)	5.3

(6.8% vs. 5.4%)		
-----------------	--	--

*Effect consistent with prior KPCO trials and systematic reviews of missed appointment interventions

Based on these calculations, a 6-month study will provide statistical power to detect a 20% relative difference in appointment loss.

Analytic plan Statistical analyses will be consistent with approaches used in prior IVR-T interventions. Patient demographic and clinical characteristics will be compared between the 2 groups using *t*-tests for normally distributed continuous variables, Wilcoxon rank tests for non-normally distributed continuous variables, and chi-square tests for discrete variables. We will assess the effectiveness of the intervention across the 3 participating clinics, after adjusting for predictors of missed appointments/late cancellations. To estimate the number of additional kept visits and available appointments per week that would result if the most effective intervention were implemented for all visits that met inclusion criteria, we will multiply the average number of visits at each clinic by the sum of the rate reduction in missed appointments and the rate increase in cancelled appointments at that clinic.

We will conduct three planned subgroup analyses:

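### The by-clinic analysis aims to inform on effect modification but specifies no treatment-by-clinic test, and the risk-quartile analysis has no treatment-by-risk test

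*Combined protocol and SAP*

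**What the plan says.** Section 10 (Analytic plan) lists three planned subgroup analyses.

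- **Analysis 1** builds a logistic model for appointment loss, with clinic as a fixed effect and an indicator for treatment group. It divides participants into risk quartiles and "will assess the effectiveness of the intervention in each quartile".
- **Analysis 2** estimates the adjusted effect in each clinic. Its declared purpose is "to provide preliminary information on site-level factors that may modify intervention effectiveness".
- **Analysis 3** estimates the effect in members who book 7 days or less ahead, because they get no reminder under the standard protocol.

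Treatment and clinic are described only as main effects. Neither the protocol nor the analysis plan mentions an interaction term, a heterogeneity test or a rule for comparing strata. Under Randomization, the plan states: "Randomization will be stratified by clinic site". Section 10 also projects gains in kept and available appointments by multiplying each clinic's volume by the absolute rate changes seen at that clinic.

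**The concern.** Whether a site factor modifies the effect is a question about the difference between clinic effects. Three separate within-clinic estimates do not answer it unless they are formally compared. Each clinic holds roughly a third of the sample, so the estimates will scatter by chance even if the true effect is the same everywhere. Without a stated comparison, the reader must set the three results side by side, by significance or by size, and both are unreliable at this sample size. The same holds for the four quartiles if anyone concludes that reminders work better in high-risk members. That conclusion would be of interest here: the background reports a stronger effect in high-risk patients in a prior primary care trial, and selective live reminders for high-risk members are planned for a later step.

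**Working it through.** **Inputs**

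- Rates and volumes (Table 1, 2018): Franklin 9.2%, 7,612; Rock Creek 4.8%, 7,592; Lone Tree 6.5%, 9,283; total 24,487.
- Effect (Table 3): 20% relative reduction, risk ratio (RR) 0.80.
- Two-sided alpha 0.05. Allocation 1:1, implied by the equal groups in Table 3.
- Size: the plan sets out "to achieve the proposed sample size of approximately 13,000 appointments", so about 6,500 per arm. The plan also says "we will limit the statistical analysis to the first randomized appointment during the project period", so the analysed number may be lower; 11,112 and 12,600 were run as well.

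**The plan's own figures first**

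The overall rate reproduces: (7,612×9.2 + 7,592×4.8 + 9,283×6.5)/24,487 = 6.81%, against the stated 6.8%.

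The Table 3 figure of 5,556 per group for 6.8% vs 5.4% does not. The standard pooled-variance formula gives 4,587; 5,556 is what it gives for 6.8% vs 8.2%. That is a separate matter. It errs on the conservative side and does not affect what follows.

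**Power within each clinic, uniform RR 0.80, N = 13,000**

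Per-arm n is 6,500 × clinic volume/24,487. Power = Φ{[|p1−p2|√n − 1.96√(2p̄(1−p̄))] / √[p1(1−p1)+p2(1−p2)]}, where p̄ is the mean of p1 and p2.

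| Clinic | n per arm | p1 vs p2 | Power |
|---|---|---|---|
| Franklin | 2,021 | 9.20% vs 7.36% | 56% |
| Rock Creek | 2,015 | 4.80% vs 3.84% | 32% |
| Lone Tree | 2,464 | 6.50% vs 5.20% | 49% |

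**Comparison by separate significance**

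Clinics are independent, and a favourable result at p<0.05 counts as significant.

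- All three significant: 0.564 × 0.322 × 0.494 = 0.090
- None significant: 0.436 × 0.678 × 0.506 = 0.149
- Split: 1 − 0.090 − 0.149 = 0.761, about 76%

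The split probability is 74% at N = 11,112, 76% at 12,600 and 77% at 15,000. It is 75% if Lone Tree's rate is taken as 5.4%, the sum of its listed components (1.2 + 1.0 + 3.2). It is 76–77% if the uniform effect is instead an odds ratio of 0.78 or a risk difference of 1.36 points.

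It depends strongly on the true effect (N = 13,000):

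| True RR | 0.60 | 0.65 | 0.70 | 0.75 | 0.80 | 0.85 | 0.90 | 1.00 |
|---|---|---|---|---|---|---|---|---|
| Split | 13% | 28% | 50% | 71% | 76% | 61% | 38% | 7% |

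**Comparison by point estimates**

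In 200,000 simulated trials with uniform RR 0.80 and N = 13,000, the largest clinic relative reduction was at least twice the smallest in about 60%. This count includes trials in which one clinic showed no reduction. The median largest and smallest clinic RRs were 0.88 and 0.72. All three clinics pointed the same way in 89%.

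**Comparison by a heterogeneity test**

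In the same setting, a 2-df treatment-by-clinic test on the log odds ratio wrongly signalled a difference in about 5% of trials (4.9%).

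Its power, over all orderings of the RRs across clinics, is 20–29% if the true RRs are 0.7, 0.8 and 0.9, and 65–84% if they are 0.6, 0.8 and 1.0. Both spreads are assumptions.

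**Quartiles**

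The documents give no quartile rates. With assumed sets averaging about 6.8%, from equal rates to 2.0/4.5/7.2/13.5%, the split probability at RR 0.80 is 82–85%.

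**The case against.** The strongest reply is that the plan never says clinics will be compared by p<0.05 in each. It speaks of assessing effectiveness and calls the clinic analysis preliminary. Read as estimates, the results would usually agree in direction. Methods are also to follow prior reminder trials, which may have used interaction tests; that cannot be checked from the documents.

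Much of this stands, and it rules out several stronger readings:

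- A reader might infer that a uniform effect would usually look different across clinics. That needs the unstated significance yardstick and a true RR between roughly 0.70 and 0.87. It fails for larger or smaller effects.
- A reader might infer that all three subgroup analyses are meant to detect effect modification. Only analysis 2 says so. Analysis 3 asks its own question, enhanced reminders against none, and the within-subgroup effect answers it.
- A reader might infer that the enhanced protocol would be kept or dropped clinic by clinic. No passage says this. The section 10 projection supposes use for all eligible visits, and the dissemination section speaks of sustaining the intervention across the organisation if it works.

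What the reply does not meet is the gap between aim and method. Calling an analysis preliminary weakens the claim made from it but does not supply a comparison. Judging by point estimates also misleads often, at about 60%.

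**Conclusion.** The point holds in a limited form. Analysis 2 has a stated aim that its stated method cannot meet, and the quartile analysis lacks the corresponding test. At the planned effect, informal comparison of clinics would suggest differences that are not there far more often than the roughly 5% of a formal test: about 76% by separate significance, about 60% by a twofold gap in estimated reductions. These figures assume Table 1 rates and volumes, 1:1 allocation, about 13,000 analysed appointments and a uniform RR of 0.80. The 76% also assumes a yardstick that the plan does not state.

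The effect scale matters too. A uniform 20% relative reduction is 1.84 points at Franklin (0.20 × 9.2), 0.96 at Rock Creek (0.20 × 4.8) and 1.30 at Lone Tree (0.20 × 6.5). It is uniform as a ratio but not on the absolute scale that the projection uses.

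The primary comparison is not affected.

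**What to change.** In section 10:

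1. Prespecify a treatment-by-clinic test (2 df) in the adjusted logistic model.
2. In a separate model, prespecify a treatment-by-risk-score test (1 df). The models should be separate because the score may itself contain clinic.
3. Base any statement that the effect differs by clinic or risk on these tests.
4. Report clinic and quartile effects with 95% CIs, labelled exploratory, not as separate significance verdicts.
5. State the effect scale, and add risk differences by clinic because the projection uses absolute rates.
6. Add a treatment-by-lead-time test only if the short-lead effect is to be compared with the effect at longer lead times.

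The cost is three interaction coefficients across two models and a few sentences, with no new data and no change to conduct. The drawback is the low power shown above. The plan should say that a non-significant interaction does not show uniformity, and that three sites cannot identify which site-level factor explains a difference.
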